6.1.1. Risk Minimization for SARS-CoV-2 Infection and Transmission

To minimize the risk of acquiring or transmitting SARS-CoV-2 infection during the study, subjects will be asked to comply with all precautionary measures related to COVID-19 stipulated within site policies and local public health guidelines or requirements.

Subjects will be provided with contact information for the clinical study site and will be given written and verbal instructions to call site personnel with any changes in their health status. They will be asked to promptly notify site personnel by phone of any positive SARS-CoV-2 testing results or symptoms/signs potentially related to COVID-19. Subjects presenting with acute illness should be medically managed according to local standard of care and per the discretion of the treating physician. Refer to Section 8.3.3 for additional guidance concerning COVID-19 vaccine deferral or discontinuation.

Subjects with laboratory confirmed SARS-CoV-2 infection should be informed as soon as possible, and should undergo medical isolation per local guidelines and CDC guidance on medical isolation ([CDC, 2021](#)), to prevent contact with others and reduce the risk of further transmission.

6.1.2. Sample Collection and Visit Scheduling for Subjects with Suspected COVID-19 Symptoms or Positive SARS-CoV-2 Test

For subjects with signs or symptoms consistent with COVID-19, or those who obtain a positive SARS-CoV-2 RT-PCR test result from another testing location, every effort should be made to obtain a sample for SARS-CoV-2 rapid RT-PCR testing as soon as possible, either during an unscheduled visit or during a planned schedule visit (whichever is sooner). All subjects with suspected COVID-19 or laboratory-confirmed SARS-CoV-2 infection will continue to follow their respective Schedule of Events (Section 9.1), as feasible according to local guidelines, site policies, and/or CDC guidance on medical isolation ([CDC, 2021](#)). Every effort should be made to obtain subsequent rapid RT-PCR testing samples as indicated in the Schedule of Events as feasible according to local guidelines, site policies, and/or CDC guidance on medical isolation ([CDC, 2021](#)). Every effort should be made to obtain subsequent rapid RT-PCR testing samples as indicated in the Schedule of Events. These samples will be banked for viral sequencing.

6.1.3. Study Stopping Rules

A Regeneron team will monitor the safety data on an ongoing basis to assess the risk-benefit profile of REGN10933+REGN10987 administered with Moderna mRNA-1273 vaccine. The team may be comprised of the medical/study director, a Global Patient Safety representative, representatives from Biostatistics and Data Management, Clinical Operations, and Regulatory Affairs.

The monitoring team will also include at least 2 medical officers from the National Institutes of Health (NIH). One officer will serve as the primary representative, with a second officer serving as an alternate representative as needed.

If there are significant safety concerns, a recommendation may be made to temporarily pause, alter, or terminate the study. Appropriate action, if needed, will be taken based upon this review and in consultation with Regeneron Safety Oversight Committee (RSOC), which will include senior clinical, regulatory, and pharmacovigilance leaders at Regeneron. Applicable regulatory procedures will be adhered to as required by local laws in relation to any decisions related to a change in study conduct, temporary halt, study termination, or study restart.

Reasons for premature withdrawal from the study are described in Section 7.3. Study drug and vaccine discontinuation rules are described in Section 8.3.2 and Section 8.3.3.

6.1.4. End of Study Definition

The end of study is defined as the date the last subject completes the last study visit, withdraws from the study, or is lost to follow-up (ie, the study subject can no longer be contacted by the investigator).

6.2. Planned Interim Analysis

Formal interim analysis may be conducted. The Sponsor may view and report on the data as it is accumulated.

7. SELECTION, WITHDRAWAL, AND REPLACEMENT OF SUBJECTS

7.1. Number of Subjects Planned

Up to approximately 286 subjects are planned to be enrolled. Refer to Section 11.2 for the justification of sample size.

7.2. Study Population

Eligible subjects for this study consist of healthy adult volunteers who are between 18 years to 90 years of age (inclusive) who are negative at screening for both SARS-CoV-2 infection and endogenous anti-SARS-CoV-2 antibodies.

Every effort should be made to enroll older subjects, such that 30% to 50% of subjects enrolled at each site are ≥ 65 years of age. Efforts should also be made to enroll subjects representative of the demographics (eg, race and ethnic distribution) of those at risk for COVID-19 in the region where the study site is located.

7.2.1. Inclusion Criteria

A subject must meet the following criteria to be eligible for inclusion in the study:

1. 18 years to 90 years of age (inclusive) at the signing of informed consent
2. Healthy or has chronic medical condition(s) that is (are) stable and well-controlled in the opinion of the investigator and that are not likely to require significant medical intervention through the end of study
3. Willing and able to comply with study visits and study-related procedures, including compliance with site precautionary requirements related to SARS-CoV-2 infection and transmission
4. Willing and able to provide signed informed consent

7.2.2. Exclusion Criteria

A subject who meets any of the following criteria will be excluded from the study:

1. Positive RT-PCR test result for SARS-CoV-2 infection at screening and/or baseline
2. Positive serology test result for anti-SARS-CoV-2 antibodies at screening
3. COVID-19 diagnosis, positive SARS-CoV-2 diagnostic test result, or positive SARS-CoV-2 serology test result at any time prior to screening
4. Previously received an investigational, authorized, or approved coronavirus vaccine (eg, SARS-CoV-2 vaccine, MERS-CoV vaccine)
5. Currently enrolled in, or has plans to enroll in, any interventional study to prevent or treat COVID-19
6. Received investigational or approved passive antibodies for SARS-CoV-2 infection prophylaxis (eg, convalescent plasma or sera, mAbs, hyperimmune globulin)
7. Received intravenous immunoglobulin (IVIG) or blood products in the last 3 months
8. Any physical examination findings and/or history of any illness that, in the opinion of the study investigator, might confound the results of the study or pose an additional risk to the subject by study participation
9. History of clinically significant cardiovascular, respiratory, hepatic, renal, gastrointestinal, endocrine, hematological, psychiatric or neurological disease, as assessed by the investigator, that may confound the results of the study or pose an additional risk to the subject by study participation
10. Medically attended acute illness or hospitalization (ie, >24 hours) for any reason within 30 days prior to screening
11. History of heart failure hospitalization, diagnosis of a myocardial infarction, stroke, transient ischemic attack, unstable angina, percutaneous or surgical revascularization procedure (coronary, carotid, or peripheral vascular), or intracardiac device placement (eg, pacemaker) within 6 months prior to screening
12. Abnormal blood pressure (BP) at screening visit, as defined by diastolic BP >100 mm Hg and/or systolic BP >160 mm Hg

Note: Blood pressure measurements may be repeated once during screening

13. Active bleeding disorder considered a contraindication to subcutaneous or intramuscular injection or phlebotomy
14. Regular alcohol consumption consistent with alcohol dependence or addiction, in the opinion of the investigator
15. Any malignancy within the past 5 years, except for basal cell or squamous epithelial cell carcinomas of the skin or carcinoma in situ of the cervix or anus, that have been resected, with no evidence of metastatic disease for 3 years

16. Immunosuppressive or immunodeficient state, asplenia or recurrent severe infections that, in the opinion of the investigator may confound the results of the study or pose an additional risk to the subject by study participation
17. Received systemic immunosuppressants or immune-modifying drugs for >14 days in total within 6 months prior to screening (for corticosteroids, ≥ 20 mg/day of prednisone equivalent)
18. History of significant multiple and/or severe allergies (eg, latex gloves), or has had an anaphylactic reaction to prescription or non-prescription drugs or food.
19. Known allergy or hypersensitivity to components of the study drug or vaccine
20. Treatment with another investigational drug within 30 days or 5 half-lives of the investigational drug, whichever is longer, prior to screening
21. Member of the clinical site study team and/or immediate family
22. Pregnant or breastfeeding women
23. Women of childbearing potential (WOCBP)¹ who are unwilling to practice highly effective contraception prior to the initial dose/start of the first treatment and for at least 6 months after REGN10933+REGN10987 administration

Highly effective contraceptive measures include:

- Abstinence^{2,3}
- Stable use of combined (estrogen and progestogen containing) hormonal contraception (oral, intravaginal, transdermal) or progestogen-only hormonal contraception (oral, injectable, implantable) associated with inhibition of ovulation initiated 2 or more menstrual cycles prior to screening
- Intrauterine device (IUD) or intrauterine hormone-releasing system (IUS)
- Bilateral tubal ligation

¹WOCBP are defined as women who are fertile following menarche until becoming postmenopausal, unless permanently sterile. Permanent sterilization methods include hysterectomy, bilateral salpingectomy, and bilateral oophorectomy.

A postmenopausal state is defined as no menses for 12 months without an alternative medical cause. A high follicle stimulating hormone (FSH) level in the postmenopausal range may be used to confirm a postmenopausal state in women not using hormonal contraception or hormonal replacement therapy. However, in the absence of 12 months of amenorrhea, a single FSH measurement is insufficient to determine the occurrence of a postmenopausal state. The above definitions are according to the Clinical Trial Facilitation Group (CTFG) guidance. Pregnancy testing and contraception are not required for women with documented hysterectomy or tubal ligation.

²Sexual abstinence is considered a highly effective method only if defined as refraining from heterosexual intercourse during the entire period of risk associated with the study drugs. The reliability of sexual abstinence needs to be evaluated in relation to the duration of the clinical trial and the preferred and usual lifestyle of the patient.

³Periodic abstinence (calendar, symptothermal, post-ovulation methods), withdrawal (coitus interruptus), spermicides only, and lactational amenorrhoea method (LAM) are not acceptable methods of contraception. Female condom and male condom should not be used together.

24. Sexually active men who are unwilling to use the following forms of medically acceptable birth control during the study drug follow-up period and for 6 months after REGN10933+REGN10987 administration: vasectomy with medical assessment of surgical success OR consistent use of a condom. Sperm donation is prohibited during the study and for up to 6 months after REGN10933+REGN10987 administration.
25. Clinical history of myocarditis and/or pericarditis.

7.3. Premature Withdrawal from the Study

A subject has the right to withdraw from the study at any time, for any reason, and without repercussion.

The investigator and/or Sponsor have the right to withdraw a subject from the study if it is no longer in the interest of the subject to continue in the study, or if the subject's continuation in the study places the scientific outcome of the study at risk (eg, if a subject does not or cannot follow study procedures). An excessive rate of withdrawals would render the study uninterpretable; therefore, unnecessary withdrawal of subjects should be avoided.

Subjects who are withdrawn prematurely from the study will be asked to complete the early termination visit, as described in Section 9.1.2.

Rules for discontinuation of study drug or vaccine are discussed in Section 8.3.

7.4. Replacement of Subjects

Subjects who do not receive their first dose of Moderna mRNA-1273 vaccine as assigned may be replaced.

8. STUDY DRUG AND COVID-19 VACCINE

8.1. Investigational Treatment (Study Drug)

In this study, the study drug (REGN10933+REGN10987) will be administered intravenously or subcutaneously as described in Section 8.5. Instructions on dose preparation are provided in the pharmacy manual. Refer to Section 9.2.2 for information on drug administration.

8.2. COVID-19 Vaccine

In this study, the vaccine (Moderna mRNA-1273) will be prepared and administered as described in the latest EUA Fact Sheet ([Moderna COVID-19 Vaccine \[HCP Fact Sheet\], 2022](#)). Refer to Section 8.5 for dose levels and method of treatment allocation; refer to Section 9.2.2 for information on vaccine administration.

8.3. Dose Modification and Discontinuation Rules

8.3.1. Dose Modification

Dose modification for an individual subject is not allowed for REGN10933+REGN10987 or Moderna mRNA-1273.

8.3.2. Study Drug Discontinuation

Subjects receiving REGN10933+REGN10987 will receive a single dose of the study drug; study drug discontinuation is not applicable.

8.3.3. Vaccine Deferral or Discontinuation

In subjects who become infected, the timing of vaccine administration (either the first dose, second dose, or booster dose, as applicable) should be deferred according to the most recent CDC guidance ([CDC, 2021](#)). Subjects who become pregnant will be counseled accordingly.

For applicable vaccine discontinuation rules, always refer to the latest Moderna mRNA-1273 vaccine EUA Fact Sheet ([Moderna COVID-19 Vaccine \[HCP Fact Sheet\], 2022](#)).

Vaccination will be permanently stopped or not administered in the event of:

- Serious or severe allergic reactions (grade ≥ 3) considered related to REGN10933+REGN10987 or Moderna mRNA-1273 vaccine

Note: In case of mild to moderate allergic reactions (grade ≤ 2) considered related to REGN10933+REGN10987 or Moderna mRNA-1273 vaccine, vaccine discontinuation is up to the investigator's discretion.

- Subject withdrawal of consent

Subjects who permanently discontinue from Moderna mRNA-1273 vaccine should be encouraged to remain in the study. Those who agree and do not withdraw from the study will be asked to return to the clinic for all remaining study follow up visits per the Schedule of Events.

Subjects who permanently discontinue and who opt to withdraw from the study will be asked to complete study assessments described in Section [9.1.2](#).

If a subject requires a prohibited medication (Section [8.8.1](#)) at any time during the study, the principal investigator should contact the Sponsor medical monitor (except for illness requiring prompt treatment). Based on the discussions, vaccination may either be continued or permanently discontinued.

8.4. Management of Acute Reactions

8.4.1. Acute Intravenous Infusion Reactions to the Study Drug

Emergency equipment and medication for the treatment of infusion reactions must be available for immediate use. All infusion reactions must be reported as AEs (as defined in Section [10.1](#)) and graded using the grading scales as instructed in Section [10.2.4](#).

8.4.1.1. Interruption of the Intravenous Infusion

The infusion should be interrupted if any of the following AEs are observed:

- Sustained/severe cough
- Rigors/chills
- Rash, pruritus (itching)
- Urticaria (hives, welts, wheals)
- Diaphoresis (sweating)
- Hypotension
- Dyspnea (shortness of breath)
- Vomiting
- Flushing

The reaction(s) should be treated symptomatically, and the infusion may be restarted at 50% of the original rate.

If investigators feel there is a medical need for treatment or discontinuation of the infusion other than described above, they should use clinical judgment to provide the appropriate response according to typical clinical practice.

8.4.1.2. Termination of the Intravenous Infusion

The infusion should be terminated and not restarted if any of the following AEs occur:

- Anaphylaxis*
- Laryngeal/pharyngeal edema
- Severe bronchospasm
- Chest pain
- Seizure
- Severe hypotension
- Other neurological symptoms (confusion, loss of consciousness, paresthesia, paralysis, etc.)
- Any other symptom or sign that, in the opinion of the investigator, warrants termination of the IV infusion

*Consider anaphylaxis if the following is observed ([Sampson, 2006](#)): acute onset of an illness (minutes to several hours) with involvement of the skin, mucosal tissue, or both (eg, generalized hives, pruritus or flushing, swollen lips-tongue-uvula) and at least one of the following:

- Respiratory compromise (eg, dyspnea, wheeze-bronchospasm, stridor, reduced peak expiratory flow, hypoxemia)

- Reduced BP or associated symptoms of end-organ dysfunction (eg, hypotonia [collapse], syncope, incontinence)

8.4.2. Acute Injection Reactions to the Study Drug

8.4.2.1. Systemic Injection Reactions

Emergency equipment and medication for the treatment of systemic reactions must be available for immediate use. All injection reactions must be reported as AEs (as defined in Section 10.1) and graded using the grading scales as instructed in Section 10.2.4.

Acute systemic reactions following SC injection of study drug should be treated using clinical judgment to determine the appropriate response according to typical clinical practice.

8.4.2.2. Local Injection Site Reactions

Local injection site reactions must be reported as AEs and graded according to Section 10.2.4.

8.4.3. Acute Injection Reactions to the Vaccine

Appropriate medical treatment to manage immediate allergic reactions must be immediately available in the event an acute anaphylactic reaction occurs following administration of the vaccine. Always refer to the latest EUA Fact Sheet ([Moderna COVID-19 Vaccine \[HCP Fact Sheet\], 2022](#)) for additional information.

8.5. Method of Enrollment and Treatment Assignment

Site-managed assignment. At screening, eligible subjects will be assigned to an enrollment wave. The enrollment waves are intended to avoid or minimize the potential for unused doses of Moderna mRNA-1273 COVID-19 vaccine (refer to Section 3.2.1 for additional rationale). Every effort should be made by sites to avoid unused doses of vaccine.

Sites will manage the placement of subjects into each wave. Every effort should be made by the site to ensure balance of age (<65 years and \geq 65 years) within each of the enrollment waves.

Randomization. At baseline (day 1), subjects will be randomized to the corresponding study arms in each wave as described in [Table 2](#).

Randomization will be performed according to a computer-generated randomization scheme provided by an interactive web response system (IWRS) to a designated study pharmacist or a qualified designee.

Randomization will be stratified by age (<65 years versus \geq 65 years).

Table 2: Study Treatment Assignment

Study Arm	Randomization Ratio	Targeted Enrollment	Co-administered REGN10933+REGN10987 Combination Therapy	Moderna mRNA-1273 Vaccine*
Enrollment Wave 1				
1	2	30	1200 mg (600 mg of each mAb) IV on day 1	On day 15 and day 43
2	2	30	300 mg (150 mg of each mAb) IV on day 1	On day 15 and day 43
3	2	30	150 mg (75 mg of each mAb) IV on day 1	On day 15 and day 43
6a	1	15	None	On day 15 and day 43
Enrollment Wave 2				
4	2	30	1200 mg (600 mg of each mAb) SC on day 1	On day 1 and day 29
5	2	30	600 mg (300 mg of each mAb) SC on day 1	On day 1 and day 29
6b	1	15	None	On day 1 and day 29
Enrollment Wave 3				
7	15	30	48 mg (24 mg of each mAb) IV on day 1	On day 15 and day 43
8	15	30	12 mg (6 mg of each mAb) IV on day 1	On day 15 and day 43
6c	4	8	None	On day 15 and day 43
Enrollment Wave 4				
9	15	30	1200 mg (600 mg of each mAb) IV on day 7	On day 1 and day 29
6d	4	8	None	On day 1 and day 29

*Moderna mRNA-1273 vaccine will be administered as described on the EUA Fact Sheet ([Moderna COVID-19 Vaccine \[HCP Fact Sheet\], 2022](#)).

mAb=monoclonal antibody; SC=subcutaneous; IV=intravenous.

8.6. Blinding

This is an open-label study without blinding.

8.7. Logistics and Accountability for Study Drug and Vaccine

8.7.1. Packaging, Labeling, and Storage

Study Drug (REGN10933+REGN10987)

Open-label study drug will display the product lot number on the label.

Study drug will be stored at the site at a temperature of 2°C to 8°C; Storage instructions will be provided in the pharmacy manual.

Vaccine (Moderna mRNA-1273)

Vaccine will be labeled and stored as described on the EUA Fact Sheet ([Moderna COVID-19 Vaccine \[HCP Fact Sheet\], 2022](#)).

8.7.2. Supply and Disposition of Study Drug

Study drug will be shipped at a temperature of 2°C to 8°C to the investigator or designee at regular intervals or as needed during the study. At specified time points during the study (eg, interim site monitoring visits), at the site close-out visit, and following drug reconciliation and documentation

by the site monitor, all opened and unopened study drug will be destroyed at the site with approval by the Sponsor or returned to the Sponsor or designee.

8.7.3. Study Drug and Vaccine Accountability

All study drug and vaccine accountability records must be kept current.

The investigator must be able to account for all opened and unopened study drug and vaccine. These records should contain the dates, quantity, and study medication

- Dispensed to each subject
- Disposed of at the site or returned to the Sponsor or designee

All accountability records must be made available for inspection by the Sponsor and regulatory agency inspectors; photocopies must be provided to the Sponsor at the conclusion of the study.

8.7.4. Study Drug and Vaccine Compliance

All drug compliance records must be kept current and made available for inspection by the Sponsor and regulatory agency inspectors.

8.8. Concomitant Medications

Any treatment administered from the time of the first dose of Moderna mRNA-1273 Vaccine or REGN10933+REGN10987 (as applicable and whichever occurs first) to the final study visit will be considered concomitant medication. This includes medications that were started before the study and are ongoing during the study.

8.8.1. Prohibited Medications and Vaccines

The use of the following concomitant medications and vaccines may not require withdrawal of the participant from the study but may determine a subject's evaluability in the per-protocol analyses (Section 11.3):

- Investigational drugs
- Investigational or approved passive antibodies for SARS-CoV-2 infection prophylaxis (eg, convalescent plasma or sera, mAbs, hyperimmune globulin)
- Any vaccine within 28 days prior to or after study drug administration, other than Moderna mRNA-1273 vaccine administered as part of this study

Exceptions:

- seasonal influenza vaccine is only prohibited within 14 days before or after study drug administration, or within 14 days before or after mRNA-1273 vaccine administration.

- COVID-19 vaccine booster vaccinations are permitted. Subjects may receive a single booster vaccination (i.e. third COVID-19 vaccine administration) in the optional Vaccine Booster Sub-study (Section 6.1). COVID-19 vaccination boosters received outside of the study are permitted and should be recorded as a concomitant medication.

- Systemic medications that suppresses the immune system (as described in Section 7.2.2 #17), except for the treatment of COVID-19

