3.1. Per Protocol Set Analysis Set (PPS)

The per protocol set (PPS) includes all randomized subjects who have received both doses of vaccine and who do not meet the following exclusion criteria:

1. Have a positive SARS-CoV-2 central serology result prior to the first dose of vaccine.
2. Receive a positive Reverse Transcription Polymerase Chain Reaction (RT-PCR) diagnostic test result for SARS-CoV-2 infection at any time point prior to the scheduled visit 56 days after the first dose of vaccine.
3. Receive any dose of investigational or approved passive antibodies for SARS-CoV-2 infection prophylaxis (eg, convalescent plasma or sera, mAbs, hyperimmune globulin) outside of the study at any time point prior to the scheduled visit 56 days after the first dose of vaccine.
4. Receive any other vaccine within 28 days prior to the study to the scheduled visit 56 days after the first dose of Moderna mRNA-1273 vaccine administered as part of this study.

Exception: seasonal influenza vaccine is only prohibited within 14 days before or after study drug administration, or within 14 days before or after Moderna mRNA-1273 vaccine administration.

5. Receive systemic medications that suppresses the immune system (for corticosteroids, ≥ 20 mg/day of prednisone equivalent) at any time point prior to the scheduled visit 56 days after the first dose of vaccine.
6. Receive IVIG or blood products at any time point prior to the scheduled visit 56 days after the first dose of vaccine.
7. Subjects with incomplete infusions or injections of study drug or vaccine at any time point prior to the scheduled visit 56 days after the first dose of vaccine.
8. Subjects with baseline neutralization antibody titer above the lower limit of quantification (LLOQ).

The PPS is the primary analysis set for assessing vaccine response related endpoints.

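### A vaccine washout that removes subjects from the primary set has no matching eligibility criterion, and in waves 1 and 3 its influenza clause excludes drug-arm subjects but keeps their concurrent controls

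*Protocol*

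**What the plan says.** Protocol 8.8.1 lists as prohibited "Any vaccine within 28 days prior to or after study drug administration, other than Moderna mRNA-1273 vaccine administered as part of this study". It says that use of a listed product "may not require withdrawal of the participant from the study but may determine a subject's evaluability in the per-protocol analyses".

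Protocol 11.3.1 names only coronavirus vaccines received outside the study among its PPS exclusions and leaves the final list to the SAP. SAP 3.1 makes the PPS the primary set for vaccine response. Its criterion 4 removes subjects who "Receive any other vaccine within 28 days prior to the study to the scheduled visit 56 days after the first dose". The exception reads: "seasonal influenza vaccine is only prohibited within 14 days before or after study drug administration, or within 14 days before or after Moderna mRNA-1273". SAP 4.4 repeats the study-drug anchor of Protocol 8.8.1.

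The only prior-vaccine item among the 25 exclusions in Protocol 7.2.2 is #4: "Previously received an investigational, authorized, or approved coronavirus vaccine (eg, SARS-CoV-2 vaccine, MERS-CoV vaccine". On replacement, Protocol 7.4 says: "Subjects who do not receive their first dose of Moderna mRNA-1273 vaccine as assigned may be replaced".

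Protocol 8.5, Table 2, gives the timing. In waves 1 and 3, study drug is given on day 1 (arms 1, 2, 3, 7, 8) and vaccine on days 15 and 43 (those arms plus 6a and 6c). In waves 2 and 4, vaccine is given on days 1 and 29, with drug on day 1 (wave 2) or day 7 (wave 4). Arms 6a to 6d receive no study drug.

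**The concern.** There are two separate gaps.

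**Eligibility.** Whether someone had another vaccine shortly before day 1 is known before randomisation. Most PPS criteria that can be met before dosing have an eligibility counterpart: RT-PCR (#1), serology (#2), passive antibodies (#6), IVIG or blood products (#7), immunosuppressants (#17). Non-coronavirus vaccines have none. A volunteer given, say, a zoster vaccine 10 days before day 1 can pass every criterion, be randomised and dosed, and then fall outside the primary analysis.

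**Unequal treatment of arms.** The influenza exception is tied to study drug, which controls never receive. Where drug precedes vaccine by 14 days, the same pre-randomisation fact excludes a subject in a drug arm and retains one in the control arm. Protocol 3.2.1.9 gives each wave its own randomised control to limit bias in arm assignment. A rule whose effect depends on assigned arm works against that aim.

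At stake are some loss of precision and a possible small bias in the primary contrasts. In addition, some volunteers would be exposed to study drug without contributing to the primary analysis.

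**Working it through.** **1. The plan's own figure.** Inputs: SD 0.30 log10, 30 per drug arm, 46 pooled controls (15+15+8+8), from Protocol 11.2 and SAP 2.2. Half-width = t(0.975; n1+n2-2) × 0.30 × √(1/n1 + 1/n2). For 30 v 46: 0.30 × √(1/30 + 1/46) = 0.0704, and multiplying by t gives 0.140 (stated 0.14). For 15 v 23, the 50%-exclusion case, it gives 0.202 (stated 0.20). Both reproduce.

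**2. Influenza windows.** Count days from day 1 (day 1 = 0) and take the union of ±14 days around each dose.

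| Wave | Drug arms | Controls | Excluded in drug arms only |
|---|---|---|---|
| 1 and 3 (drug 0; vaccine 14, 42) | -14 to 56 | 0 to 56 | -14 to -1 (14 days) |
| 2 (drug 0; vaccine 0, 28) | -14 to 42 | -14 to 42 | none |
| 4 (drug 6; vaccine 0, 28) | -14 to 42 | -14 to 42 | none |

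With the -1 to +3 day visit window for the first vaccine dose, the 14 days become 13 to 17. Planned subjects exposed to the unequal rule: 5 × 30 = 150 in the drug arms and 15 + 8 = 23 in 6a and 6c. These are numbers at risk, not numbers affected.

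**3. Precision.** Let f be the share of subjects given influenza vaccine in the 14 days before day 1. The documents give no value, so 5% to 20% is an assumption. Each drug arm keeps 30(1-f). Arms 6a and 6c keep all 23. Arms 6b and 6d keep 23(1-f).

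| f | Lost per drug arm | Lost over arms 1, 2, 3, 7, 8 | Lost from 6a+6c | Half-width v pooled control |
|---|---|---|---|---|
| 0 | 0 | 0 | 0 | 0.140 |
| 5% | 1.5 | 7.5 | 0 | 0.143 (28.5 v 44.85) |
| 10% | 3 | 15 | 0 | 0.147 (27 v 43.7) |
| 20% | 6 | 30 | 0 | 0.154 (24 v 41.4) |

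**4. Bias.** Let d be the titer difference, on the log10 scale, between recent influenza vaccinees and other subjects. A range of 0.1 to 0.3 is also an assumption. Against the concurrent control (6a or 6c) the bias is f × d, from 0.05 × 0.1 = 0.005 to 0.20 × 0.3 = 0.06. Against pooled control it is [23/(23 + 23(1-f))] × f × d:
- low end: 0.513 × 0.05 × 0.1 = 0.0026 (GMT ratio factor 1.006)
- high end: 0.556 × 0.20 × 0.3 = 0.033 (factor 1.08)

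If recent vaccinees have higher titers, the retained controls make the drug arms look worse. If they have lower titers, the reverse holds.

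**5. Anchors side by side.** For vaccines other than influenza, SAP 3.1 counts back from the study, which is the same for all arms but is not defined as consent, screening or day 1. Protocol 8.8.1 and SAP 4.4 count from study drug, which has no date in 6a to 6d. These texts need to be reconciled.

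**The case against.** The case against has substance.

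- **Not lost to the study.** A reader might infer that these subjects are wasted. They are not: they stay in the safety set and, if centrally seronegative at baseline, in the mFAS. SAP 5.7.4 allows efficacy variables to be explored in the mFAS. Drug-arm subjects with samples also stay in the PK and ADA sets.
- **The asymmetry is narrow.** A reader might infer that the whole washout treats arms unequally. Under SAP 3.1 the 28-day rule for other vaccines does not. Only the influenza exception does, and only in waves 1 and 3.
- **The primary contrast is not within wave.** SAP 5.7.1 pools all four control arms. The supplementary analysis in SAP 5.7.5 is optional and groups waves 1-2 and 3-4. The PPS is already not a strict randomised comparison: Protocol 11.3.1 makes it as treated, and SAP 3.1 criterion 7 excludes incomplete study-drug administration, which only drug arms can have. So it goes too far to say that the rule breaks the planned randomised comparison.
- **Sites are warned.** Protocol 8.8.1 lists these vaccines, and 8.8.2 sends concomitant-medication questions to the medical monitor. No document shows that such enrolment happened. The supported statement is that sites can dose such subjects.
- **Replacement.** Protocol 7.4 provides for one case and is silent on others. It makes no provision for these subjects but does not expressly forbid replacing them.
- **Size.** The study is descriptive, and the precision loss lies well inside the planned 50%-exclusion case.

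These points limit the size and scope of the finding. They do not supply the missing eligibility line or give the control arms a day-1 anchor.

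**Conclusion.** Both gaps stand on the text. SAP 3.1 criterion 4 removes subjects from the primary set on information available before randomisation, and Protocol 7.2.2 does not screen for it. Followed literally, the influenza clause applies a pre-randomisation exclusion according to assigned arm in waves 1 and 3. Definite removal comes from the SAP; the protocol alone says only that evaluability may be affected.

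The likely consequence is small: at most about 0.014 log10 on the half-width (0.140 to 0.154) and a bias against pooled control of up to about 0.033 log10. Both figures rest on assumed values of f and d. There is no bias if recent influenza vaccinees have the same day-56 titers as other subjects, and the documents give no evidence either way. The point deserves correction because the inconsistency is clear and cheap to remove, not because it threatens the study's conclusions.

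**What to change.** 1. In SAP 3.1 criterion 4, SAP 4.4 and Protocol 8.8.1, anchor the pre-dose part of the 28-day and 14-day windows on study day 1 for every arm. This replaces the study and study drug administration as anchors.
2. Report PPS exclusions under this criterion by arm.
3. Reconcile Protocol 7.2.2 with the rule by carrying the documents' own 28-day and 14-day windows into eligibility for any subjects still to be enrolled. SAP 2.1 describes randomisation in the past tense, so this step may no longer change who enters. Steps 1 and 2 are useful either way.

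**Cost.** Without the eligibility line, re-anchoring also removes some controls from 6a and 6c. At f = 5%, 10% and 20% that is 23 × f = 1.2, 2.3 and 4.6 subjects, and the half-width against pooled control becomes 0.144, 0.148 and 0.158, against 0.143, 0.147 and 0.154 under the current rule. With the eligibility line applied to everyone, 30 and 46 are kept and it stays at 0.140. Some candidates would need re-screening, since a 28-day wait exceeds the 21-day screening period.
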